8.6.2 Secondary and Exploratory Endpoints

For secondary endpoints, due to the limited sample size in the study, descriptive statistics with mean and 95% confidence intervals will be used. For continuous variables, descriptive statistics will include the number of non-missing values, mean, standard deviation, median, min and maximum. For categorical variables, descriptive statistics will include counts and percentages per category. For comparison between subgroups, ANOVA and t-tests will be used when appropriate to determine the association of the efficacy endpoints and specific biomarkers.

8.6.2.1 Safety

Safety events will be summarized based on frequency and proportion of total subjects, by system organ class and preferred term. Separate summaries with descriptive statistics will be presented according to anatomic subtype of biliary cancer (e.g. intrahepatic, hilar/perihilar, extrahepatic, GBC).

8.6.2.2 Tumor PD-L1 Expression Rate

The proportion of subjects overall and according to anatomic subtype with archival tumor samples positive for PD-L1 expression using the protocol-defined central IHC assay (QualTek Laboratories) (see Section 4.3.5.3.1) will be reported along with 95% CI. For subjects with more than one tumor sample available for testing, designation as positive for PD-L1 expression will be based upon ≥ 1 positive sample. With an expected evaluable sample size of approximately 36 tumor samples adequate for PD-L1 testing expected out of planned 42 total enrollment in the study, assuming 40% of tumors will be PD-L1+ expression, we will be able to estimate the 95%CI of the PD-L1+ expression as 27.7% - 53.9%. Concordance and rates of positivity between primary and metastatic site, tumor location (e.g. liver vs. non-liver), and pre- and post-treatment samples will be described individually due to expectation of small subset/paired sample sizes.

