3.2 Secondary Objective(s) & Hypothesis (es)

- (1) **Objective:** Measure safety (NCI CTCAE v.4.0) for the novel combination overall and according to anatomic subtype.

Hypothesis: The combination is safe and feasible with $\leq 50\%$ related \geq grade 3 toxicity rate (Common Terminology Criteria for Adverse Events (CTCAE) version 4.0) during first 3 cycles (completion of Induction Phase plus 1 additional cycle).

(2) **Objective:** Determine proportion PD-L1+ overall.

Hypothesis: Approximately 40% of tumors will be PD-L1+ overall based upon PD-L1+ rates observed in KEYNOTE-028 biliary cohort.⁵

(3) **Objective:** Determine overall response rate (ORR) by RECIST 1.1¹ according to PD-L1 status.

Hypothesis: The ORR by RECIST 1.1 will be higher in PD-L1+ biliary cancers compared to PD-L1- tumors.

(4) **Objective:** Determine proportion with progression-free survival at 6 months (%PFS6) overall and according to PD-L1 status.

Hypothesis: In advanced biliary tract cancer patients after failure of 1st-line chemotherapy, pembrolizumab plus induction GM-CSF will achieve proportion with PFS at 6 months of 40% (H_1), a meaningful proportion compared to 20% (H_0) in historical controls treated with conventional 2nd line chemotherapy.

(5) **Objective:** Measure median duration of response (DOR), PFS, and OS in overall cohort and according to PD-L1 status.

Hypothesis: The median OS in overall cohort will be improved compared to historical control OS of approximately 6.7 months from start of treatment with 2nd line chemotherapy for advanced biliary cancer.⁶

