4.3.6.4 Biomarker Research

4.3.6.4.1 Tumor and TIIC PD-L1 Expression by Immunohistochemistry (IHC)

Tumor and/or TIIC PD-L1 expression by IHC are associated with an increased likelihood of response to immune checkpoint inhibition with PD-1 inhibitors in some cancer types.³⁸ A pooled analysis of 20 trials including 1475 patients with melanoma, non-small cell lung cancer (NSCLC), and genitourinary cancer showed a significant interaction between PD-L1 expression and response overall, with overall RR 34.1% vs. 19.9% (p<0.0001).³⁸ Response rates were significantly higher in PD-L1+ melanoma and NSCLC but no significant difference in response rate was observed according to PD-L1 status for genitourinary cancers, and a significant proportion of patients with PD-L1-negative tumors achieved tumor response to PD-1 inhibition across tumor types.

It is not known whether tumor PD-L1 expression is a predictive biomarker for response in biliary cancers, as the KEYNOTE-028 biliary cohort required PD-L1 expression for eligibility⁵ and the unselected KEYNOTE-158 biliary cohort results have not been reported. Intra-tumoral spatial and temporal heterogeneity in PD-L1 expression may also confound interpretation of tumor PD-L1 expression in archival pre-treatment samples which, in some cases, may have been harvested long before start of treatment.

Priming by an induction course of GM-CSF could also induce expression of PD-L1 in tumors or in TIIC such as tumor-associated lymphoid cells or monocytes, as has been demonstrated with administration of GVAX in pancreatic tumors.³¹

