Based upon these findings which suggest that pre-treatment tumor PD-L1 expression may not be essential for response to treatment with the combination of pembrolizumab plus induction GM-CSF, tumor PD-L1 expression by IHC is not required as an integral biomarker for eligibility but will be tested as an integrated biomarker and secondary objective. Archival tumor biopsy or resection samples will be accessioned and tested centrally in batch at end of study for PD-L1 expression using an approved IHC assay (QualTek Laboratories). It is expected that the majority of samples will have been obtained pre-treatment. Treatment history at time of tumor sampling for each case will be documented in case report forms (CRFs), and an exploratory analysis may be conducted to compare proportion with PD-L1 expression based upon whether sample was obtained pre-treatment or after treatment with prior chemotherapy. An exploratory analysis will also be performed to compare tumor PD-L1 status in primary versus metastatic sites and according to anatomic location of the primary biliary cancer (e.g., intrahepatic CCA, extrahepatic CCA, GBC) or the metastatic site (e.g., liver vs. non-liver).

Paired primary and metastatic site tumor samples from the same patient will be tested and described when available. On-treatment or post-treatment tumor samples will also be analyzed if available in cases for which tumor resection or biopsy is required for clinical care (e.g. palliative metastatectomy, biopsy of an equivocal lesion to confirm progression, or if fiducial placement is required for palliative radiotherapy). PD-L1 expression will also be measured in on-treatment tumor biopsy samples obtained on pembrolizumab therapy and on combination therapy in patients enrolled to the Expansion Cohort.

4.3.6.4.2 Peripheral Blood Mononuclear Cell (PBMC) Immune Cell Subsets, TCR Clonotype Frequency and Diversity, and Other Analyses

Research blood samples will be collected from all patients at baseline, at multiple time points during treatment, and at progression (see Section 6.0 – Study Flow Chart). Whole blood will be processed into PBMC and cryopreserved at the UCSF Immune Monitoring Core for future analyses in batch at completion of study, pending funding and if warranted based upon clinical outcomes.

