4.3.6.4.3 Tumor Infiltrating Immune Cell (TIIC) Numbers and Profiles Pre-Treatment and On-Treatment

Preexisting tumor immune infiltration is associated with increased likelihood of tumor response to checkpoint inhibition.^{41,42} This association between tumor immune infiltration and increased response to immunotherapy may be due to preexisting tumor-specific T cell clones within the tumor which have been primed by tumor antigens but attenuated by checkpoint signaling, which are then activated upon checkpoint inhibition.

To explore the impact of tumor immune infiltration in biliary cancers treated with the combination of pembrolizumab plus induction GM-CSF, archival pre-treatment tumor core biopsy or resection samples (primary and/or non-nodal metastatic site depending on availability) will be obtained when available. Pending funding and adequate sample size, the samples may be examined in batch for immune cell infiltrates (TIIC) and T cell subset composition in batch at study completion in the laboratory of [name] at UCSF as has been previously described.^{33,39,43} The presence of TIIC and immune cell subset composition will be explored for association with clinical outcomes including PFS, ORR, DOR, OS, and CA 19-9- response.

If available from a standard of care tissue sampling event, , such as in cases for which an on-treatment or post-treatment tumor resection or biopsy is required for clinical care (e.g. palliative metastatectomy/debulking, biopsy of an equivocal lesion, or if fiducial placement is required for palliative radiotherapy), paired archival on-treatment or post-treatment tumor samples will also be analyzed in comparison to the baseline/pre-treatment specimen.

In the Expansion Cohort, paired biopsies will be obtained on pembrolizumab and on pembrolizumab plus GM-CSF to ascertain the relative impact of pembrolizumab alone compared to pre-treatment archival sample, then the impact of addition of GM-CSF to pembrolizumab compared to pre-treatment and compared to pembrolizumab monotherapy. It is expected that GM-CSF effect will be apparent after 2 weeks of exposure based upon tumor tissue analyses showing increased tumor T cell infiltration in prostate cancer patients treated with GM-CSF prior to radical prostatectomy.¹²

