h	Cross-sectional imaging with CT or MRI abdomen plus pelvis (including triphasic/multiphase liver preferred) and CT chest with/ or without contrast is required at screening, every 8 weeks (±7 days) during treatment for first 6 months then every 8 weeks (±14 days) after 6 months on treatment until end of treatment. In subjects without evidence progression at treatment discontinuation, scans should be every 8 weeks ±28 days for up to 1 year during Follow-Up Phase, then every 12 weeks ± 28 days (or more often if clinically indicated). Imaging may be performed more often if clinically indicated to evaluate for progression or toxicity. Imaging should be performed as close to time of Safety Follow-Up visit as possible in cases of discontinuation after confirmed response or completion of 24 months of treatment.														
i	CA 19-9 should be checked at same time points as imaging. Note that CA 19-9 may be elevated due to biliary obstruction/stent occlusion independent of progression. CA 19-9 testing may be performed more often if clinically indicated to evaluate for progression.														
j	Archival tumor samples (FFPE block when available and/or at least 10 unstained slides of approximately 10 µm thickness plus a paired H&E slide) should be obtained from prior tumor sampling/diagnostic procedure(s) such as prior resection, core biopsy, or cytology/cell button when available. FFPE block or slides should also be obtained from any subsequent tumor sampling which occurs during or after protocol therapy (such as repeat biopsy to confirm progression or palliative metastatectomy surgery). See Appendix 11.6.														
k	Blood samples will be obtained in all patients for PBMC immune profiling at Screening, on Day 1, 8, and 15 of Cycle 1, on Cycle 2 Day 1, Cycle 3 Day 1, then Q8 weeks ± 14 days during subsequent cycles through C9D1. Screening sample may be used for Cycle 1, Day 1 if obtained within 3 days. Samples will be obtained at time of Safety Follow-Up visit (PBMC collection at this time-point may be omitted or delayed until next UCSF clinic visit if patient has Safety Follow-Up Visit assessments performed outside of UCSF), and at time of progression if patient discontinued treatment without progression and is identified with progression during Follow-Up. See Appendix 11.6.														

UCSF Helen Diller Family Comprehensive Cancer Center

Version date: 10/01/2019

Protocol CC#: 154524

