7.1.4.1 Archival Tumor Tissue Collection

In all patients, left-over diagnostic tumor block and/or slides from any tumor sampling procedure(s) (e.g. biopsy, fine needle aspiration, cytology brushings, and/or resection specimens) performed prior to enrollment, during study treatment, and/or during the Follow-Up Phase will be obtained to determine tumor PD-L1 expression status, to characterize tumor immune infiltrates/T cell subsets, and (optional) to bank for future correlative analyses as part of the UCSF Hepatobiliary Tissue Bank and Registry (CC#124512) as a companion protocol to this study. Formalin-fixed, paraffin-embedded (FFPE) tumor tissue blocks will be accessioned whenever available. In addition to blocks or if a block is not available, at least 10 unstained slides (prefer 10 μ m) plus 1 H&E slide from a tumor tissue block may be accessioned. Corresponding pathology reports from initial diagnosis and/or subsequent tumor sampling will be obtained. Specimens will be obtained from the Pathology Department for banking as soon as possible after consent and/or occurrence of post-enrollment tumor sampling and stored the Helen Diller Family Comprehensive Cancer Center (HDFCCC) Tissue Core (UCSF patients). Correlative analyses using archival tissue samples will be performed in batch at completion of study and pending funding. See Appendix 11.6 for correlative specimen procurement and handling instructions.

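### The any-positive rule for PD-L1 status has no cut-off at first dose, so the status used for secondary objectives 2 to 5 is not strictly a baseline factor

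*Combined protocol and SAP*

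**What the plan says.** Section 3.2 uses PD-L1 status in secondary objectives 2 to 5: its prevalence (expected to be about 40%), then ORR, PFS6, DOR, PFS and OS by status. Objective 3 has a directional hypothesis: "The ORR by RECIST 1.1 will be higher in PD-L1+ biliary cancers compared to PD-L1- tumors".

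Section 8.3.2(2) defines status as positive or negative by central IHC with pre-specified cut-points and gives no timing. Section 8.6.2.2 reports "The proportion of subjects overall and according to anatomic subtype with archival tumor samples positive for PD-L1 expression" and adds that, with more than one sample, "designation as positive for PD-L1 expression will be based upon ≥ 1 positive sample".

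Several places show which tissue is meant:

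- Section 7.1.4.1, on archival tissue, covers leftover material from procedures "performed prior to enrollment, during study treatment, and/or during the Follow-Up Phase will be obtained to determine tumor PD-L1 expression status".
- Section 4.3.6.4.3 says that "paired archival on-treatment or post-treatment tumor samples will also be analyzed in comparison to the baseline/pre-treatment specimen".
- The archival-tissue footnote in Section 6.1 says "FFPE block or slides should also be obtained from any subsequent tumor sampling which occurs during or after protocol therapy". Sections 6.2 and 6.4 repeat it.
- Section 4.3.6.4.1 says "Priming by an induction course of GM-CSF could also induce expression of PD-L1 in tumors or in TIIC". For the Expansion Cohort it adds that "PD-L1 expression will also be measured in on-treatment tumor biopsy samples obtained on pembrolizumab therapy and on combination therapy".

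**The concern.** A factor used to split patients for response and survival should be fixed before treatment. Here the label can change afterwards, and the protocol itself gives a mechanism by which study treatment could change it. Extra tissue is also not obtained at random. It comes from events after baseline, such as palliative resection, biopsy of an equivocal lesion or fiducial placement.

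Two things are at stake. The first is the prevalence estimate, which is set against an external benchmark. The second is the meaning of every comparison by PD-L1 status, because the label may partly reflect how the patient fared.

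**Working it through.** **Does the word archival already limit the rule to baseline?** No. Sections 7.1.4.1 and 4.3.6.4.3 both apply it to tissue taken on or after treatment. Where pre-treatment tissue is meant, the protocol says so (objectives 3.3(5) and 3.4); Section 8.6.2.2 leaves the qualifier out.

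**The plan's own figure.** Section 8.6.2.2 gives a 95% CI of 27.7% to 53.9% for 40% prevalence with 36 evaluable. The Wald interval is 0.40 ± 1.96 × √(0.40 × 0.60/36) = 24.0% to 56.0%. Wilson gives 25.7% to 56.2% and Clopper-Pearson 24.1% to 57.6%. None matches. The printed interval is close to a 90% Wilson interval (27.7% to 53.7%). This is a separate correction, but the true width, about 30 points, is the yardstick for what follows.

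**Inputs from the documents.** 36 of 42 evaluable and 40% prevalence (8.6.2.2); at least 12 of 15 Expansion patients with paired biopsies (11.6.3); overall ORR 20% (3.1).

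**Assumptions.** The share f of patients with on-treatment tissue (5 of 36 for clinical tissue; 12 of 36 if the research pair counts), the number k of added samples, and the chance c that an added sample from a baseline-negative patient tests positive. The documents give no conversion rate.

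**Prevalence.** Any-positive prevalence = p + f(1 − p)[1 − (1 − c)^k], with p = 0.40.

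| Tissue counted | c | Rise in prevalence |
|---|---|---|
| Clinical: f = 5/36, k = 1 | 10% | 5/36 × 0.6 × 0.10 = 0.8 points |
| Clinical: f = 5/36, k = 1 | 50% | 5/36 × 0.6 × 0.50 = 4.2 points |
| Research pair: f = 12/36, k = 2 | 10% | 12/36 × 0.6 × 0.19 = 3.8 points |
| Research pair: f = 12/36, k = 2 | 25% | 12/36 × 0.6 × 0.4375 = 8.8 points |
| Research pair: f = 12/36, k = 2 | 40% | 12/36 × 0.6 × 0.64 = 12.8 points |

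No term can be negative, so the direction is fixed.

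**ORR by status, no true association, research biopsies counted.** Assume all responders but only 60% of non-responders reach the second biopsy.

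*Conversion 25% in everyone.*
- Positive among biopsied responders: 0.4 + 0.6 × 0.4375 = 0.6625.
- Positive among biopsied non-responders: 0.6 × 0.6625 + 0.4 × (0.4 + 0.6 × 0.25) = 0.6175.
- Over all 36, with two thirds unbiopsied at 0.40: 0.4875 and 0.4725.
- ORR in PD-L1+: 0.2 × 0.4875/(0.2 × 0.4875 + 0.8 × 0.4725) = 20.5%.
- ORR in PD-L1−: 0.2 × 0.5125/(0.2 × 0.5125 + 0.8 × 0.5275) = 19.5%.

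*Conversion 40% in responders, 15% in non-responders.*
- Biopsied responders: 0.4 + 0.6 × 0.64 = 0.784.
- Biopsied non-responders: 0.6 × 0.5665 + 0.4 × 0.49 = 0.5359.
- Over all 36: 0.528 and 0.4453.
- ORR 22.9% in PD-L1+ and 17.5% in PD-L1−.

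**The distortion can also run the other way.** Both cases use one added sample and c = 30%.

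- *Dilution.* True ORR 30% versus 13.3%, with 12 of 36 sampled regardless of response. Converted patients make up 0.6 × 1/3 × 0.3 = 0.06, so ORR in PD-L1+ is (0.4 × 0.30 + 0.06 × 0.133)/0.46 = 27.8%. The gap shrinks from 16.7 to 14.5 points.
- *Tissue taken more often from non-responders.* No true association, tissue in 27% of responders and 35% of non-responders. Positive proportions are 0.4486 and 0.463, so ORR is 19.5% in PD-L1+ and 20.4% in PD-L1−.

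**The case against.** The best defence is that the intent is visible. Section 4.3.6.4.1 introduces the biomarker by reference to pre-treatment expression, expects most samples to be pre-treatment, and treats later samples as an addition. Section 8.6.2.2 describes pre- and post-treatment samples individually. Section 7.1.4.1 is a collection section with several purposes, not a status definition. This shows what was probably meant, but none of it restricts the designation. The expectation about pre-treatment samples is also ambiguous, because the same paragraph contrasts pre-treatment with samples taken after prior chemotherapy.

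A reader might infer that the Expansion research biopsies feed the status. No section says so. Objective 3.4(1) lists them apart from archival samples, Section 6.4 gives them their own row, and Section 7.1.4.3 assigns them to exploratory endpoints. This part of the objection stands, and the larger figures above are therefore conditional.

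A reader might also infer that the ORR hypothesis is pushed toward being true, with immortal-time bias in PFS and OS the same way. The documents do not support a fixed direction. The clinical samples they name include biopsies to confirm progression and fiducials for palliative radiotherapy, which would tend to come from patients doing badly. Section 8.6.2.4 moreover specifies DOR, PFS and OS overall and by anatomic subtype only, so the comparisons by PD-L1 status in objective 5 have no detailed analysis to assess.

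Finally, working only within biopsied patients gives much larger gaps (27% versus 10%, or 21% versus 18%, on the same assumptions). Objective 3 concerns the study population, where those gaps are 22.9% versus 17.5% and 20.5% versus 19.5%.

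**Conclusion.** The concern holds in a limited form. As written, the rule lets leftover clinical tissue taken on treatment or in Follow-Up set a status that objectives 2 to 5 use as a tumor characteristic. Prevalence bias is upward only: about 1 to 4 points for clinical tissue alone, and about 4 to 13 points if the research pairs counted. The first range is small beside a 95% interval about 30 points wide; the second is not negligible. If the 60% second-biopsy assumption is also applied to prevalence, 0.2 + 0.8 × 0.6 = 0.68 of biopsied patients have two biopsies. The rise is then 0.2 × [0.68(1 − (1 − c)²) + 0.32c], or 3.2, 7.6 and 11.3 points for c = 10%, 25% and 40%.

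Distortion of outcomes by status has no fixed direction. With no true association and research biopsies counted, the study-wide ORR gap is about 1 to 5 points. All these sizes rest on assumed conversion and sampling rates. The affected analyses are secondary and mainly descriptive; the primary ORR does not use PD-L1 status.

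**What to change.** In Sections 8.3.2(2) and 8.6.2.2:

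1. Define PD-L1 status for secondary objectives 2 to 5 from tissue taken before the first dose of study treatment, in those terms, since pre-treatment can be read as before earlier chemotherapy.
2. Apply the any-positive rule only among pre-dose samples.
3. State that Expansion research biopsies and all other post-dose tissue do not feed the status, and report them only descriptively, as paired change from the pre-dose sample.

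The cost is wording. Under Section 4.3.6.4.1, archival tissue is tested in batch at the end of the study and treatment history at sampling is recorded on the CRF, so no new procedure is needed. The downside is that a subject with only post-dose tissue has unknown status; the number of such subjects should be reported.

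### The planned 95% CI of 27.7%–53.9% for PD-L1 positivity does not follow from about 36 samples at 40%; it is about 4 to 7 points too narrow in total width, and no interval method is named

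*Combined protocol and SAP*

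**What the plan says.** Section 3.2, secondary objective 2, sets the working assumption: "Approximately 40% of tumors will be PD-L1+ overall". Section 8.6.2.2 says the proportion of subjects with a PD-L1-positive archival sample, overall and by anatomic subtype, "will be reported along with 95% CI". It then gives the planned precision. The inputs are an "expected evaluable sample size of approximately 36 tumor samples adequate for PD-L1 testing", "expected out of planned 42 total enrollment in the study", and 40% positivity. The result is that "we will be able to estimate the 95%CI of the PD-L1+ expression as 27.7% - 53.9" percent.

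The unit of analysis is the subject: someone with several samples counts once, as positive if at least one sample is positive. No interval method is given in that section. Section 8.6.2 adds only that for secondary endpoints "descriptive statistics with mean and 95% confidence intervals will be used". Fisher's exact test is named in several places, but for tests and power rather than for intervals.

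**The concern.** The sample size, the assumed proportion, the confidence level and the resulting interval all stand in one sentence, so the result can be checked directly. A standard error near 8 points (about 36 subjects at 40%) implies a 95% interval some 30 points wide or more. The plan states 26.2.

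At stake is how precisely the trial can claim to estimate the PD-L1-positive fraction. This sentence is the plan's only statement on that, and it promises more precision than the design delivers. Because no method is named, the reader also cannot tell which calculation was intended.

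**Working it through.** **Inputs (all from section 8.6.2.2).** n = 36, p = 0.40 (so x = np = 14.4), two-sided 95% level (z = 1.96). Stated limits 27.7 and 53.9: width 53.9 − 27.7 = 26.2 points, midpoint 40.8.

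**Step 1: try to reproduce the stated interval at n = 36, p = 0.40.**

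*Wald:* p ± z√(p(1−p)/n). The standard error is √(0.24/36) = 0.0816; 1.96 × 0.0816 = 0.160. Limits 24.0–56.0, width 32.0.

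*Wilson:* centre (x + z²/2)/(n + z²) = (14.4 + 1.92)/(36 + 3.84) = 16.32/39.84 = 0.4096. Half-width z√(np(1−p) + z²/4)/(n + z²) = 1.96 × √(8.64 + 0.96)/39.84 = 0.1524. Limits 25.7–56.2, width 30.5.

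*Clopper-Pearson:* the 2.5% quantile of Beta(x, n−x+1) = Beta(14.4, 22.6) and the 97.5% quantile of Beta(x+1, n−x) = Beta(15.4, 21.6). Limits 24.1–57.6, width 33.5.

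| 95% method, n = 36, 40% | Limits (%) | Width | Wider than stated by |
|---|---|---|---|
| Stated in plan | 27.7–53.9 | 26.2 | – |
| Wilson | 25.7–56.2 | 30.5 | 4.3 |
| Agresti-Coull | 25.7–56.2 | 30.5 | 4.3 |
| Jeffreys | 25.3–56.3 | 31.0 | 4.8 |
| Logit | 25.5–56.5 | 31.0 | 4.8 |
| Arcsine | 24.8–56.3 | 31.4 | 5.2 |
| Wald | 24.0–56.0 | 32.0 | 5.8 |
| Clopper-Pearson | 24.1–57.6 | 33.5 | 7.3 |

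A continuity-corrected Wald interval (22.6–57.4, width 34.8) is further away still. The stated figure is not reproduced. Limit by limit, Wilson differs by 27.7 − 25.7 = 2.0 and 56.2 − 53.9 = 2.3 points; Clopper-Pearson by 27.7 − 24.1 = 3.6 and 57.6 − 53.9 = 3.7 points.

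**Step 2: whole counts.** 40% of 36 is not a whole number. At 14/36, Wilson gives 24.8–55.1 and Clopper-Pearson 23.1–56.5. At 15/36, Wilson gives 27.1–57.8 and Clopper-Pearson 25.5–59.2. Neither count gives the stated limits.

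**Step 3: a larger n within the trial.** The subject is the unit and 42 is the planned total, so n cannot exceed 42. At n = 42 and 40%, Wilson gives 26.6–55.0, Wald 25.2–54.8 and Clopper-Pearson 25.2–56.2. Over every n from 36 to 42 and every whole count within 2.5 points of 40%, the narrowest 95% interval is 28.2 points (Wilson, 16/42), still 28.2 − 26.2 = 2.0 points wider than stated.

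**Step 4: the n that the stated width implies.** For Wald, n = z²p(1−p)/(half-width)² = 3.84 × 0.24/0.131² ≈ 53.7, so 54. The same question gives 51 for Wilson and 59 for Clopper-Pearson. All exceed planned enrollment.

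**Step 5: can the source be identified?** No. A 90% interval at n = 36 and 40% comes close (Wilson 27.7–53.7), but so does a 95% interval at 20/50 (Wilson 27.6–53.8). A search over n = 30 to 79, all whole counts, the eight methods above, at 95% and 90%, found no case that matches both limits to one decimal.

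**The case against.** The strongest reply concerns consequence, and it largely stands. The sentence is illustrative, built on an approximate sample count and an assumed rate. Sample size rests on ORR, with PFS6 as key secondary (section 8.4.1). PD-L1 status is not an eligibility criterion, secondary endpoints are descriptive, and the reported interval will use the observed counts. Nothing downstream inherits the error.

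It is also fair to say that the 4 to 7 points are total width, that the error in any single limit is smaller, and that the range is the one spanned by Wilson, Wald and Clopper-Pearson. The missing method is a lesser matter: at n = 36 and 40%, Wilson and Clopper-Pearson limits differ by less than 2 points (25.7 against 24.1; 56.2 against 57.6). On its own that would be missing detail rather than a mistake, although the choice will matter more for the smaller anatomic subtypes, for which intervals are also promised.

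None of this makes the stated interval correct for its own inputs. The word "approximately" does not help either, because even the full enrollment of 42 leaves the interval too wide to match.

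**Conclusion.** The stated interval is wrong for the sample size, proportion and confidence level given beside it. Its width of 26.2 points compares with 30.5 (Wilson) to 33.5 (Clopper-Pearson), so planned precision is overstated by 4.3 to 7.3 points in total width.

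This rests on a two-sided 95% interval for a single proportion, one result per subject, about 36 subjects and a 40% rate, all as the plan states them. It does not depend on which standard method was meant. How the error arose cannot be settled from the documents. The matter is minor: it affects a descriptive precision statement and no decision.

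**What to change.** In section 8.6.2.2, restate the expected 95% CI at 36 samples and 40% as about 26%–56% (Wilson) or 24%–58% (Clopper-Pearson). Name the method that will be used for the reported interval, overall and by subtype. If the authors meant a different confidence level or sample count, they should state that and give the interval that matches. The cost is one sentence of SAP wording; the only drawback is a less favourable stated precision.

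A separate, optional clarification, not an error: the rule that one positive sample makes a subject positive could say that it uses only tissue taken before the first dose. Section 7.1.4.1 says tissue from procedures "performed prior to enrollment, during study treatment, and/or during the Follow-Up Phase will be obtained to determine tumor PD-L1 expression status". Section 4.3.6.4.1, however, treats later tissue as an addition ("On-treatment or post-treatment tumor samples will also be analyzed if available"), and section 8.6.2.2 describes pre- and post-treatment samples individually, so the intended reading is probably already pre-treatment.
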